1.2. Schema

					Patients - Length of Tre	~450 patien atment= ~'							
Day 1		Dose 1 Do M1		Dose 3 M 4	Dose M6		Dose 5 M8		Dose 6 M10		Dose 7 M12		
Scree		CAB +	RPV LA 2M									Extension Phase	
1 mon	BL Surv Intervie			Interim Survey						Su	of Stud Irvey & Irviews	,	
					Clinical S Providers (Sites (n = ~ min ~ 3 per							
		Site Initiation											
		M1	M2	M3 M4	M5 M6	M7	M8	M9	M10	M11	M12	M13	,
estigator Aeeting	SWAT CQI, SDM		inced Imple	ementation Arm	ı (Arm-e)								
		BL Surv Intervie			Interim Survey Interview	/ &					nd of St Survey Interview	&	
vestigator Meeting	r MSL, SDM		dard Imple	ementation Arm	- (Arm-s)								

OLI = Oral Lead In, M=Month CAB = Cabotegravir, RPV = Rilpivirine, CQI = Continuous Quality Improvement; BL = Baseline, SWAT=Skilled Wrap Around Team; CQI= Continuous Quality Improvement; SDM= Study Delivery Meeting; MSL= Medical Science Liaison

1.3. Schedule of Activities (SoA)

Table 1 Schedule of Activities for Patient Study Participants

		Intervention Period (Month)									Sa						
Procedure	Screening ^a up to 35d	Screenii up to 3:	Screenii up to 3:	Screenir up to 35	Screenii up to 3:	Screenii up to 3:	Day 1	Month 1	Month 2	Month 4	Month 6	Month 8	Month 10 ^b	Month 12 b	Withdrawal ^m	Safety Follow-up Visit ^w	 Long Term Follow-up ⁿ
		Oral Lead- in	Dose 1 (D1)	Dose 2 (D2)	Dose 3 (D3)	Dose 4 (D4)	Dose 5 (D5)	Dose 6 (D6)	Dose 7 (D7)	val ^m	w-up	p"					
Written Informed consent	Х																
Eligibility Verification	X																
Demography	X																
Physical Exam	X										Xw						
Medical history	X																
Current medical conditions	X																
Center for Disease Control and Prevention (CDC) HIV- 1 Classification	X																
Syphilis serology + reflex Rapid Plasma Reagin (RPR)	X																
Injection site reaction (ISR) assessment			X	X	X	X	X	X	X	X	X	X					

213199

]		Sa						
Procedure	Screening ^s up to 35d	Day 1	Month 1	Month 2	Month 4	Month 6	h Month 8 Month 10 b Month 12 b	Withdrawal ^m	Safety Follow-up Visit ^w	- Long Term Follow-up ⁿ -		
	5d	Oral Lead- in	Dose 1 (D1)	Dose 2 (D2)	Dose 3 (D3)	Dose 4 (D4)	Dose 5 (D5)	Dose 6 (D6)	Dose 7 (D7)	valm	dn-mo	p m
Symptom Directed Physical Exam and Medical Assessment ^c		x	X		X		X		X	X		X
HIV-associated Conditions, AE and serious adverse event (SAE) Assessments ^d , Con Meds	x	x	X		X		X		X	X	x	x
Vital Signs (blood pressure [BP], heart rate [HR]) ^e	X	X	X		X		X		X	X		
Weight, Height & body mass index (BMI) ^f	X	X	X		X		X		X	X		
Clinical Chemistry, Hematology and other Tests ^o	x	x	X	X	X		X		X	X	Xw	X
HIV-1 RNA and plasma sample for storage ^h	X	X	X	X	X		X		X	X		X
CD4+ count	X	X	X	X	X		X		X	X		X

213199

]	-	Sat						
Procedure	Screening ^a up to 35d	Day 1	1 Month 1	h Month 2	Month 4	Month 6	Month 8	Month 10 b	Month 12 b	Withdrawal ^m	Safety Follow-up Visit ^w	- Long Term Follow-up ⁿ
		Oral Lead- in	Dose 1 (D1)	Dose 2 (D2)	Dose 3 (D3)	Dose 4 (D4)	Dose 5 (D5)	Dose 6 (D6)	Dose 7 (D7)			
CD8+ cell count (will be reported at Baseline and Month 12)		x							X			
Urinalysis	X									X		X
Hepatitis Serology ^q	X											
Whole Blood PBMC ^p		X								X		
Prothrombin time (PT)/ partial thromboplastin time (PTT)/international normalized ratio (INR)	x											
Pregnancy Testing Urine (U) or Serum ^g	U	U	U	U	U	U	U	U	U	U		U
Notification of Interview ^t		x										
Oral CAB + RPV Medication Dispensation		X										
CAB LA + RPV LA IM Treatment Administration ⁱ			X	X	X	X	X	X	X			

213199

]		Sa						
Procedure	Screening* up to 35d	Day 1	Month 1	Month 2	Month 4	Month 6	Month 8	Month 10 b	Month 12 b	Withdrawal ^m	Safety Follow-up Visit ^w	Long Term Follow-up ⁿ
	Δ. ř	Oral Lead- in	Dose 1 (D1)	Dose 2 (D2)	Dose 3 (D3)	Dose 4 (D4)	Dose 5 (D5)	Dose 6 (D6)	Dose 7 (D7)	/alm		D B
Participant Visit Reminder Contact	х	х	х	х	х	х	х	х				
Participant Contact Detail Confirmation	x	х	х	х	х	х	х	х				
Patient Toolkit ^s		х	х	х	х			X				
Record Visit Length ^j			х	х		х	х					
Contraception Counseling ^u										х		x
HAART dispensation ^v										х		X
Patient Questionnaires ^k			X		X				х			
Selected Patient Interviews ¹		х							х			
CCI												

213199

	Screening ^a up to 35d		Intervention Period (Month)								Safe	
Procedure		Day 1	1 Month 1	Month 2	Month 4	Month 6	Month 8	Month 10	Month 12	Withdrawa1 ^m	ety Follo Visit ^w	- Long Term Follow-up ⁿ
		Oral Lead- in	Dose 1 (D1)	Dose 2 (D2)	Dose 3 (D3)	Dose 4 (D4)	Dose 5 (D5)	Dose 6 (D6)	Dose 7 (D7)		dn-wo	ip"
Preference Question									X			
Review plan to transition to commercial product or alternative ART ^v											Х	

a) A screening visit will be conducted within 35 days of Day 1. However, it is preferred for Day 1 to be conducted as soon as practical after all screening results are available.

- b) Continue this pattern for visits for the remainder of the study if needed, until CAB LA + RPV LA is locally approved and available. For example, Dose 8 will be conducted as per Dose 6, Dose 9 will be conducted as per Dose 7, Dose 10 will be conducted as per Dose 6 and so on. The exception to this pattern is that no questionnaires, study visit length collection, or patient interviews will be conducted after Dose 7 visit. Visit after Month 12 will be considered, 'extension phase.' See Section 6.8.
- c) Physical exams should be conducted as part of normal routine clinical care but data will not be collected in the electronic case report form (eCRF) unless abnormalities are observed. Medical assessments include any decisions the study staff must make for participant management.
- d) AE and SAEs will not be proactively assessed at M 2, M 6 and M 10. However, all AEs and SAEs reported by study participants **must** be recorded in eCRF at all visits and reported within required timelines as per Section 8.5.1.
- e) Measure vital signs after about 5 minutes of rest in a semi-supine position.
- f) Height and body mass index (BMI) are collected at screening only.
- g) A (-) urine pregnancy test is required prior to oral lead-in at day 1 and prior to any injection and as required by Medical Monitor after a treatment interruption. A (+) urine test should be confirmed with a stat serum test. If (+), participant will need to be withdrawn. A Serum pregnancy test should be performed at any time pregnancy is suspected by the Investigator. Pregnant participants who remain in the study do not need pregnancy testing for the duration of the pregnancy see Appendix 15: Information and Guidance for Managing Pregnant Participants.
- h) Plasma for storage samples are collected for possible future analyses. Can be used for back-up in cases of loss/damage in transit, geno/pheno analyses for virologic failures. Only for women becoming pregnant and continuing on CAB LA+RPV LA as if pregnant a plasma HIV-1 RNA test and plasma for storage samples at Month 6 and Month 10 visits are required.
- i) All injections are 1 x CAB LA 600 mg IM + 1 x RPV LA 900 mg IM. Doses 1 and 2 are one month apart. Subsequent injections beginning at Dose 3 are every two months. The injections should be spaced approximately 2 cm from one another and from the site of any previous injection and/or any injection site

reaction. Bring RPV LA to approximately room temperature prior to injecting. Time and location of injection (right or left) as well as needle length used will be collected in the eCRF. IM dosing is expected to occur on the same date of the month as determined by IM Dose 1 visit date, this is the Target Date; where possible, this first injection should be performed within 2 hours of taking the last oral regimen dose. For Dose 2, a dosing window of +0 / -7 days from the target visit date is stipulated. A (+ or -) 7-day window from the target date visit is stipulated for IM dosing beginning at Dose 3. All decisions regarding dose interruption/ resumption must be discussed with the Medical Monitor in advance.

- Length of study visit from arrival until departure from clinic will be evaluated. Participant's time of arrival, actual start time of the appointment, and actual end time of the appointment will be collected in the eCRF.
- k) Questionnaires should be completed before receiving the injections.
- Interviews should be conducted before the PSP receives Dose 1 and within 4 weeks of receiving Dose 7. Interviews may be done in person, virtually, or by phone. A minimum of 6 patients per site will be selected for interviews.
- m) Withdrawal Visit Conduct ~4 weeks after the last dose of investigational product (IP) if not entering Long-Term Follow Up and only if the participant has ongoing AEs or lab abnormalities at the last on-study visit. If visit is not possible ensure a safety follow-up visit is completed.
- n) Participants receiving one or more injections with CAB LA and/or RPV LA will be assessed with clinic visits at months 3, 6, 9 and 12 during the Long-Term Follow-Up phase. The start of the 52-week follow-up period begins the day of the last CAB LA and/or RPV LA dose.
- See Section 8.4.4 for list of tests
- p) Whole blood/PBMC collection samples may be used for virologic analyses. PBMCs will be collected at baseline Day1 and at Withdrawal.
- q) Hepatitis B (HBsAg), Anti-HBc, Anti-HBsAg, Hepatitis C (anti-HCVAb). A (+) anti-HCVAb will be followed by a confirmatory nucleic acid test for HCV RNA. HBV DNA will only be performed for participants with a (+) anti-HBc and (-) HBsAg and (-) anti-HBs (past and/or current evidence).
- r)

- t) Notification of interviews may occur between Day 1 or during the 7 days after Day 1.
- Women of childbearing potential should continue to receive counselling on the need to use adequate contraception for the entirety of the Long-Term Follow-Up period.
- Investigators must discuss choice of HAART regimen and timing of initiation with the Medical Monitor before initiating.
- w) Required when a patient study participant leaves the study following commercial availability of IP, or, if an on-site withdrawal visit is not possible and there are ongoing AEs, SAEs related and not related to study drug, or any laboratory abnormalities that are considered to be AEs or are potentially harmful to the participant, at the last on-study visit. Should be conducted approximately 2-4 weeks after the last dose of IP. Can be completed by remotely, if applicable and tests needed to be done at clinic may not be performed.

s) At a minimum the study toolkit will be offered at the time pointed noted in the Table 6. However, the toolkit items are intended to be used throughout the study.

TMF-13794092

CONFIDENTIAL

213199

								Tin	ne (Month	ıs)					
Assessments	Both Arms	arm- e Only	1ª	2	3	4	5	6	7	8	9	10	11	12	Until end of study
Informed Consent ^g	X														
Questionnaire	X		X ^b				X ^c							X ^d	
Interviews (SSI)	X		X ^b				Xc							X ^d	
CQI Calls ^e		X	Initial SWAT	X	X	X	X	X	X						
SWAT ^f		X	Meeting and Intro to CQI												
FRAME-IS	X			X	X	X	X	X	X	X	X	X	X	X	
CSAT	X													X	
Provider Toolkit ^h	X		X	X	X	X	X	X	X	X	X	X	X	X	X

Table 2 Schedule of Assessments Table for Staff Study Participants

a) Month 1 starts at site activation

b) Questionnaire and interview should be conducted prior to the site's first patient receiving their first CAB LA + RPV LA injection at that site.

c) Questionnaire and interview should be conducted within approximately 4 weeks of the site's first patient receiving their third injection.

d) Questionnaire and interviews should be conducted within approximately 4 weeks of the site's first patient receiving their last injection.

e) Intro to CQI calls will occur within four weeks of site activation. Additional CQI calls will be scheduled if deemed necessary.

f)Initial SWAT meeting will occur within four weeks of site activation. Additional SWAT meetings with each site will occur as needed throughout the study.

g) Informed consent will be obtained prior to any study assessments (where applicable, as determined by local regulatory and compliance requirements).

h) At a minimum the study toolkit will be offered at the time pointed noted in the Table 6. However, the toolkit items are intended to be used throughout the study.

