8.4. Safety Assessments- Patient Study Participants

8.4.1. Clinical Evaluations

The following clinical evaluations will be performed according to the schedule of activities:

- Monitoring and recording of all AEs and SAEs. Additional information on the Time Period and Frequency of Detecting AEs and SAEs is provided in Section 1.3.
- Physical exams should be conducted as part of normal routine clinical care. Abnormalities noted during any exam must be recorded in the eCRF (e.g., in the current medical conditions or AE logs).
- Height and weight will be measured and recorded. Height collected on the Day 1 (Baseline) only.
- Vital signs will include systolic and diastolic blood pressure and heart rate collected after resting for about 5 minutes. Temperature will also be collected.
- Past medical history, family history, social history, medication history. Targeted history on cardiovascular risk (smoking history, family and personal history).

- HIV-associated conditions will be recorded.
- Regular monitoring of hematology, blood chemistry and glucose (parameters to be tested listed below).
- Pregnancy testing. A negative urine pregnancy test is required prior to initiation of IP, any dose of CAB LA or RPV LA or as required by the Medical Monitor following a treatment interruption(s). If serum testing is required locally, the results should be available prior to the visit where urine testing is indicated per the Schedule of Activities.
 - Participants who are enrolled in the study and have a positive pregnancy test during the course of the study, will be allowed to remain in the study, provided a pregnancy specific ICF addendum is signed by the participant. No IP can be continued (oral or LA) in any pregnant participant until the benefit/risk assessment is discussed with the participant and the pregnancy specific ICF addendum has been signed. See details in Appendix 15: Information and Guidance for Managing Pregnant Participants.
 - Pregnant participants who remain in the study do not need pregnancy testing during the study, for the duration of their pregnancy.
- Evaluation and documentation of all concomitant medications and blood products.
- Injection Site Reactions (ISRs) will be assessed clinically during the study for the following:

Pain, tenderness, pruritis, warmth, bruising, discoloration, infections, rash, erythema, swelling, induration, and nodules (granulomas or cysts).

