8.5.5. Pregnancy

8.5.5.1. Pregnancy Testing

Women of childbearing potential must have a negative pregnancy test at Screening, and at Baseline (Day 1). Pregnancy testing will also be conducted as per the Schedule of Activities (Section 1.3) and at any time during the trial when pregnancy is suspected.

If pregnancy is confirmed, a discussion with the pregnant study participant assessing the benefit/risk assessment of continuing in the study will be undertaken. If, after this discussion, the participant would like to continue in the study, this will be allowed, provided the pregnant participant signs the pregnancy specific ICF addendum. See Section 10.15 for details.

Pregnant participants who remain in the study do not need pregnancy testing during the study, for the duration of their pregnancy. Additionally, the Medical Monitor may request that a urine pregnancy test be performed in the event of a treatment interruption greater than 7 days.

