8.5.5.2. Rationale for Continued Use in Pregnancy

Additional data regarding the use of CAB + RPV LA during pregnancy, and management of pregnant participants remaining in the study are found in Appendix 15: Information and Guidance for Managing Pregnant Participants

The use of CAB + RPV LA during pregnancy may offer unique benefits. It is well documented that treatment adherence challenges to oral therapy exists both in the peripartum and post-partum periods with LA dosing offering a unique opportunity to overcome such adherence challenges. LA therapy may also help with nausea (50 % mild to moderate) or hyperemesis (2%) that is frequently seen, especially during the first trimester of gestation.

Participants on LA dosing who become pregnant will have exposures throughout pregnancy due to the long half-life and PK tail of CAB/RPV. Prior to this protocol amendment, pregnant participants would have been withdrawn from the study, and initiated on an alternative oral ART regimen. Alternative regimens consist of either 2 or 3 antiretrovirals to protect the life of the mother and for the prevention of MTCT. This regimen, combined with the long half-life and PK tail of CAB/RPV, would potentially expose the fetus to additional ARVs during gestation (in some cases upwards of 5 antiretrovirals).

Given the risk/benefit ratio for cabotegravir and rilpivirine LA dosing in WOCBP, coupled with concerns of increasing fetal exposure to several additional antiretrovirals upon participant withdrawal, this amendment to the protocol will allow pregnant participants to remain in the study after a pregnancy specific ICF addendum is signed by the participant.

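### Table 1 footnote g still orders withdrawal after any confirmed positive pregnancy test, which contradicts the current rule for pregnancies that arise during study treatment

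*Protocol*

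**What the plan says.** Footnote g to Table 1 (Protocol Section 1.3) requires a negative urine test before oral lead-in and before any injection, and a serum test to confirm a positive. It then says "If (+), participant will need to be withdrawn". No visit, phase or consent condition is attached. The same footnote ends: "Pregnant participants who remain in the study do not need pregnancy testing for the duration of the pregnancy", with a pointer to Appendix 15. Footnote h sets extra viral load sampling at Months 6 and 10 and introduces it with "Only for women becoming pregnant and continuing on CAB LA+RPV LA".

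The body of the protocol distinguishes by timing.

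- **Before treatment.** Section 8.5.5.1: "Women of childbearing potential must have a negative pregnancy test at Screening, and at Baseline (Day 1". Sections 5.1 and 5.2 exclude pregnant women.
- **During the study.** Section 8.4.1 says a participant with a positive test "will be allowed to remain in the study, provided a pregnancy specific ICF addendum is signed by the participant". It also covers the oral product: "No IP can be continued (oral or LA) in any pregnant participant until the benefit/risk assessment is discussed with the participant". Section 8.5.5.2 gives the reason and says "this amendment to the protocol will allow pregnant participants to remain in the study after a pregnancy specific ICF addendum is signed by the participant". Sections 8.5.5.1 and 10.7.1 and Appendix 15 (10.15.1 and 10.15.6) say the same.
- **Discontinuation reasons.** Section 7 lists pregnancy neither among the reasons that may lead to discontinuation nor among those that must.

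The SAP copies the withdrawal sentence in its own schedule (Section 13.1.1, footnote g), while SAP Section 11.1.2 states that pregnant participants may stay on study drug.

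**The concern.** A coordinator holding a positive test is likely to read the footnote on that row of the schedule, and there the withdrawal order comes before the pointer to Appendix 15. Section 8 makes the Schedule of Activities binding and allows waivers only for urgent safety action, so the sentence works as an instruction.

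If it is followed for a pregnancy arising on treatment, the participant could be taken out without the benefit/risk discussion and the choice to continue that Section 8.5.5.1 gives her. The viral load at every visit during pregnancy (Section 10.15.6) and the pre-injection drug concentrations (Section 10.15.6.2) could also be lost; these feed SAP Listings 52, 56 and 57. If she has had an LA dose and is switched to oral therapy, the fetus could be exposed to further antiretrovirals on top of the residual LA drugs. Section 8.5.5.2 gives avoiding that as a reason for the amendment.

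**Working it through.** This is a comparison of passages of current text with each other. It does not rest on the amendment summary.

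**Which text is out of date.** Section 8.5.5.2 states that withdrawal was the practice before this amendment and that the amendment replaces it. Footnote g therefore keeps the former rule. Its last sentence and footnote h reflect the new rule, so the footnotes do not agree among themselves.

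**Where the conflict bites.** The row "Pregnancy Testing Urine (U) or Serum" in Table 1 is marked in 11 columns; the Safety Follow-up column is blank.

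| Columns | Number | Effect of the sentence |
|---|---|---|
| Screening, Day 1 | 2 | Right in effect: not eligible |
| Month 1 | 1 | Conflicts, on narrower grounds |
| Months 2, 4, 6, 8, 10, 12 | 6 | Clear conflict: at least one LA dose given |
| Withdrawal; LTFU (months 3, 6, 9, 12) | 2 | No study drug left to stop |

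Check: 2 + 1 + 6 + 2 = 11.

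At Month 1 the test precedes the first injection. Appendix 15 and Section 10.7.1 speak of continuing LA dosing, so the conflict there rests on Section 8.4.1, which names oral as well as LA product, and on the general wording of Section 8.5.5.1. The argument about residual LA exposure does not apply at that visit. Footnote b carries the visit pattern into the Extension Phase, so the clear conflict continues there.

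**How many cases.** Inputs: the goal of 20% female participants (Section 1.1); 450 evaluable and 474 enrolled (Section 9.2); and a contraceptive failure rate below 1% per year with consistent and correct use (Section 10.7, Table 17).

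- Women at the goal: 0.20 × 450 = 90; 0.20 × 474 = 94.8, about 95.
- Upper limit on expected pregnancies per year: 90 × 0.01 = 0.90; 95 × 0.01 = 0.95.

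This assumes that every woman is of childbearing potential, which overstates the number at risk, and that contraception is used correctly, which may understate the rate. The documents give no typical-use rate, and 20% is a goal rather than a cap.

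**The case against.** The strongest reply is that this is an editorial slip. The correct rule is stated in several sections, footnote g itself points to Appendix 15, and cases will be few. The investigator should inform the sponsor within 24 hours of learning of a pregnancy (Section 8.5.5.4), and the choice of follow-on therapy must be discussed with the Medical Monitor before it is started (Section 4.3.4). Much of this stands: an error is possible, not certain, and it may be caught before any switch. It does not make the sentence harmless, because it is a wrong instruction in a binding schedule on the care of pregnant participants.

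A reader might infer more than the documents support on three points.

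- *That Section 7 contradicts the footnote outright.* It is silent. It agrees with the newer sections only in not listing pregnancy as a reason to discontinue.
- *That the mistake could not be undone.* Section 7.2 calls study discontinuation permanent, but footnote g says only that the participant is withdrawn. Section 8.5.5.3 sends a woman who has had an LA dose and does not continue during pregnancy into long-term follow-up, where viral load is still measured, and pregnancy outcome is still collected. The bar on re-screening adds nothing during pregnancy, which is itself exclusionary.
- *That withdrawal necessarily adds fetal drug exposure.* Where marketed LA product is locally available, a participant leaving the study may move to it (Sections 4.3.4 and 4.5.1.2). Added exposure follows only from a switch to oral therapy.

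A request to exempt continuing participants from the negative test before injection would also be largely met already, by the last sentence of footnote g and by Sections 8.4.1 and 8.5.5.1.

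**Conclusion.** The inconsistency is real and should be corrected. For a positive test during study treatment, footnote g gives the pre-amendment rule and contradicts Sections 8.4.1, 8.5.5 and 10.7.1, Appendix 15, its own last sentence and footnote h. The case is clearest at six scheduled visits and in the Extension Phase, and narrower at Month 1. What is at risk is a participant's discussion and choice, and some planned viral load and drug-concentration data. Added fetal exposure is possible but conditional.

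It would be wrong to read this as an unsettled design: the intended rule is clear, and one sentence misstates it. Nor does it touch the trial's results, since no power, sample-size or endpoint figure depends on it. The expectation of few cases rests on correct contraceptive use and on the female enrolment goal being roughly met. The SAP copy gives no instruction to sites and matters only for consistency.

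**What to change.** Replace the withdrawal sentence in footnote g with wording such as:

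> If (+) at Screening or Day 1 before the first dose, the participant is not eligible and must not start study treatment. If (+) while receiving study treatment (oral or LA), give no further IP until the benefit/risk discussion is held and the pregnancy-specific ICF addendum is signed; manage per Sections 8.4.1, 8.5.5 and Appendix 15, including participants who decline to continue. If (+) at a Withdrawal or LTFU visit, report and follow the pregnancy per Section 8.5.5.

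Send sites a short note with the correction, and make the same edit in SAP Section 13.1.1. The cost is one footnote, one site communication and one matching SAP edit. Design, sample size and analysis stay as they are.
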